Subjects who restart treatment will be retreated at the same dose and dose interval as when they last received pembrolizumab. Treatment will be administered for up to one additional year.

Visit requirements are outlined in Section 6.0 – Schedule of Events.

7.12 Dose modification and toxicity management for immune-related AEs associated with pembrolizumab

Pembrolizumab

AEs associated with pembrolizumab exposure may represent an immunologic etiology. These immune-related AEs (irAEs) may occur shortly after the first dose or several months after the last dose of pembrolizumab treatment and may affect more than one body system simultaneously. Therefore, early recognition and initiation of treatment is critical to reduce complications. Based on existing clinical trial data, most irAEs were reversible and could be managed with interruptions of pembrolizumab, administration of corticosteroids and/or other supportive care. For suspected irAEs, ensure adequate evaluation to confirm etiology or exclude other causes. Additional procedures or tests such as bronchoscopy, endoscopy, skin biopsy may be included as part of the evaluation. Based on the severity of irAEs, withhold or permanently discontinue pembrolizumab and administer corticosteroids. Dose modification and toxicity management guidelines for irAEs associated with pembrolizumab are provided in Table 6.

Table 6 Dose Modification and Toxicity Management Guidelines for Immune-related AEs Associated with Pembrolizumab

General instructions:				

 1. Corticosteroid taper should be initiated upon AE improving to Grade 1 or less and continue to taper over at least 4 weeks. 2. For situations where pembrolizumab has been withheld, pembrolizumab can be resumed after AE has been reduced to Grade 1 or 0 and corticosteroid has been tapered. Pembrolizumab should be permanently discontinued if AE does not resolve within 12 weeks of last dose or corticosteroids cannot be reduced to ≤ 10 mg prednisone or equivalent per day within 12 weeks. 3. For severe and life-threatening irAEs, IV corticosteroid should be initiated first followed by oral steroid. Other immunosuppressive treatment should be initiated if irAEs cannot be controlled by corticosteroids. 				
Immune-related AEs	Toxicity grade or conditions (CTCAEv4.0)	Action taken to pembrolizumab	irAE management with corticosteroid and/or other therapies	Monitor and follow-up

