Pneumonitis	Grade 2	Withhold	
 • Administer corticosteroids (initial dose of 1-2 mg/kg prednisone or equivalent) followed by taper 	
 • Monitor participants for signs and symptoms of pneumonitis • Evaluate participants with suspected pneumonitis with radiographic imaging and initiate corticosteroid treatment • Add prophylactic antibiotics for opportunistic infections
	Grade 3 or 4, or recurrent Grade 2	Permanently discontinue		
Diarrhea / Colitis	Grade 2 or 3	Withhold	
 • Administer corticosteroids (initial dose of 1-2 mg/kg prednisone or equivalent) followed by taper 	
 • Monitor participants for signs and symptoms of enterocolitis (ie, diarrhea, abdominal pain, blood or mucus in stool with or without fever) and of bowel

	Grade 4	Permanently discontinue		
perforation (ie, peritoneal signs and ileus).
 
 Participants with \geq Grade 2 diarrhea suspecting colitis should consider GI consultation and performing endoscopy to rule out colitis. Participants with diarrhea/colitis should be advised to drink liberal quantities of clear fluids. If sufficient oral fluid intake is not feasible, fluid and electrolytes should be substituted via IV infusion.
AST / ALT elevation or Increased bilirubin	Grade 2	Withhold	
 Administer corticosteroids (initial dose of 0.5- 1 mg/kg prednisone or equivalent) followed by taper 	
 Monitor with liver function tests (consider weekly or more frequently until liver enzyme value returned to baseline or is stable)
	Grade 3 or 4	Permanently discontinue	
 Administer corticosteroids (initial dose of 1-2 mg/kg prednisone or equivalent) followed by taper 	
Type 1 diabetes mellitus (T1DM) or Hyperglycemia	Newly onset T1DM or Grade 3 or 4 hyperglycemia associated with evidence of β -cell failure	Withhold	
 Initiate insulin replacement therapy for participants with T1DM Administer anti-hyperglycemic in participants with hyperglycemia 	
 Monitor participants for hyperglycemia or other signs and symptoms of diabetes.

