9.5 Rescue Medications & Supportive Care

9.5.1 Supportive Care Guidelines

Subjects should receive appropriate supportive care measures as deemed necessary by the treating investigator. Suggested supportive care measures for the management of adverse events with potential immunologic etiology are outlined below and in greater detail in the ECI guidance document. Where appropriate, these guidelines include the use of oral or intravenous treatment with corticosteroids as well as additional anti-inflammatory agents if symptoms do not improve with administration of corticosteroids. Note that several courses of steroid tapering may be necessary as symptoms may worsen when the steroid dose is decreased. For each disorder, attempts should be made to rule out other causes such as metastatic disease or bacterial or viral infection, which might require additional supportive care. The treatment guidelines are intended to be applied when the investigator determines the events to be related to pembrolizumab.

Note: if after the evaluation the event is determined not to be related, the investigator is instructed to follow the ECI reporting guidance but does not need to follow the treatment

guidance (as outlined in the ECI guidance document). Refer to Section 7.12 for dose modification.

It may be necessary to perform conditional procedures such as bronchoscopy, endoscopy, or skin photography as part of evaluation of the event. Suggested conditional procedures, as appropriate, can be found in the ECI guidance document.

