9.5.2 Expected AEs due to Pembrolizumab and Guidelines for Management

- **Pneumonitis:**

- For **Grade 2 events**, treat with systemic corticosteroids. When symptoms improve to Grade 1 or less, steroid taper should be started and continued over no less than 4 weeks.
- For **Grade 3-4 events**, immediately treat with intravenous steroids. Administer additional anti-inflammatory measures, as needed.
- Add prophylactic antibiotics for opportunistic infections in the case of prolonged steroid administration.

- **Diarrhea/Colitis:**

Subjects should be carefully monitored for signs and symptoms of enterocolitis (such as diarrhea, abdominal pain, blood or mucus in stool, with or without fever) and of bowel perforation (such as peritoneal signs and ileus).

- All subjects who experience diarrhea/colitis should be advised to drink liberal quantities of clear fluids. If sufficient oral fluid intake is not feasible, fluid and electrolytes should be substituted via IV infusion. For Grade 2 or higher diarrhea, consider GI consultation and endoscopy to confirm or rule out colitis.
- For **Grade 2 diarrhea/colitis** that persists greater than 3 days, administer oral corticosteroids.
- For **Grade 3 or 4 diarrhea/colitis** that persists > 1 week, treat with intravenous steroids followed by high dose oral steroids.
- When symptoms improve to Grade 1 or less, steroid taper should be started and continued over no less than 4 weeks.

- **Type 1 diabetes mellitus (if new onset, including diabetic ketoacidosis [DKA]) or ≥ Grade 3 Hyperglycemia, if associated with ketosis (ketonuria) or metabolic acidosis (DKA)**

- For **T1DM or Grade 3-4 Hyperglycemia**
 - Insulin replacement therapy is recommended for Type I diabetes mellitus and for Grade 3-4 hyperglycemia associated with metabolic acidosis or ketonuria.
 - Evaluate subjects with serum glucose and a metabolic panel, urine ketones, glycosylated hemoglobin, and C-peptide.

- **Hypophysitis:**

- For **Grade 2 events**, treat with corticosteroids. When symptoms improve to Grade 1 or less, steroid taper should be started and continued over no less than

- 4 weeks. Replacement of appropriate hormones may be required as the steroid dose is tapered.

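### Section 9.5.2 makes grade 3-4 pembrolizumab-related diarrhea/colitis wait longer for steroids (more than 1 week) than grade 2 (more than 3 days), which does not fit Section 7.12

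*Combined protocol and SAP*

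**What the plan says.** Section 9.5.2 sets steroid triggers for diarrhea/colitis by grade. For a grade 2 event "that persists greater than 3 days, administer oral corticosteroids". For a grade 3 or 4 event "that persists > 1 week, treat with intravenous steroids followed by high dose oral steroids". It gives no steroid instruction for a grade 3-4 event during the first week. The same entry asks for monitoring for bowel perforation.

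Section 7.12 also covers steroid treatment of immune-related events. Its text says: "Based on the severity of irAEs, withhold or permanently discontinue pembrolizumab and administer corticosteroids". It also says that "early recognition and initiation of treatment is critical to reduce complications". It then names the operative table: "Dose modification and toxicity management guidelines for irAEs associated with pembrolizumab are provided in Table 6". General instruction 3 of Table 6 reads: "For severe and life-threatening irAEs, IV corticosteroid should be initiated first followed by oral steroid". The steroid entry in the diarrhea/colitis row, beside grade 2 or 3, reads: "Administer corticosteroids (initial dose of 1-2 mg/kg prednisone or equivalent) followed by taper". It carries no persistence condition.

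Section 9.5.1 describes the standing of the 9.5 measures: "Suggested supportive care measures for the management of adverse events with potential immunologic etiology are outlined below". It refers the reader to Section 7.12 for dose modification and to a separate events-of-clinical-interest (ECI) guidance document for more detail.

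**The concern.** A steroid trigger should not lengthen as the event gets worse. Table 9 defines grade 3 as severe, with hospital admission indicated, and grade 4 as life-threatening, with urgent intervention indicated. A condition of more than a week sits badly with both definitions and with the emphasis on early treatment in Section 7.12.

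Subject safety is at stake. Section 9.5.2 is where a treating physician would look for event-by-event steroid instructions. One who takes the bullet at face value could hold steroids for more than a week in severe colitis, a condition in which the same section asks staff to watch for perforation.

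**Working it through.** The plan states no figure to reproduce. The check sets the two sections side by side and counts the comparable instructions.

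**1. Steroid trigger for diarrhea/colitis, by source**

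| Grade | Section 9.5.2 | Section 7.12 and Table 6 |
|---|---|---|
| 2 | Oral steroids after more than 3 days | 1-2 mg/kg prednisone or equivalent, then taper; no persistence condition |
| 3 | IV, then high-dose oral, after more than 7 days | Same row entry as grade 2; general instruction 3 adds IV first for severe events; no persistence condition |
| 4 | As grade 3 | General instruction 3: IV first for life-threatening events; no persistence condition |

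The grade 4 steroid cell in the Table 6 colitis row is blank in the text as read from the PDF. It may be a merged cell, so the grade 4 comparison rests on general instruction 3 alone.

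**2. Size of the inversion in 9.5.2**

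Grade 3-4 trigger minus grade 2 trigger: 7 days − 3 days = 4 days longer for the more severe grade.

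**3. Is a wait normal for grade 3-4 events in 9.5.2?**

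The events with a grade 3-4 steroid instruction are:

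- pneumonitis: IV steroids at once
- diarrhea/colitis: IV steroids after more than 1 week
- hypophysitis: IV then oral, no wait
- hyperthyroidism: IV then oral, no wait
- hepatic: IV for 24 to 48 hours, which is a treatment duration and not a wait
- renal: systemic steroids, no wait

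That makes 6 events, of which 1 carries a persistence condition. Myocarditis is not counted because its steroid instruction has no grade. Type 1 diabetes/hyperglycemia and the severe skin reactions are not counted because 9.5.2 gives no steroid instruction for them.

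**4. Does any text reconcile the two sections?**

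None was found. The 9.5.1 cross-reference to Section 7.12 concerns dose modification, not when steroids start. Sections 5.4.1 and 9.1 stop treatment at an attributed grade 3 or greater event, and Table 6 withholds pembrolizumab at grade 2 or 3 colitis and discontinues it at grade 4. These rules govern drug exposure and do not set steroid timing. The ECI guidance document was not available.

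**The case against.** The strongest reply is that the two sections can be followed together. Section 7.12 gives no start time, and its silence is not an order to treat at once. General instruction 3 mainly fixes the order of routes, IV then oral, and the 9.5.2 bullet gives the same order. Section 7.12 also asks for evaluation to confirm the cause, and 9.5.1 asks staff to rule out infection. The 9.5 measures are suggestions, supportive care is left to the treating investigator, and nothing forbids earlier steroids. Pembrolizumab is withheld or stopped in any case. The unseen ECI document may give a different rule.

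Much of this stands, and it rules out several stronger readings that a reader might infer:

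- *That the protocol bars steroids in the first week.* It does not; it only fails to call for them in the colitis bullet.
- *That Section 7.12 orders an immediate start, so the sections flatly contradict each other.* Section 7.12 bases steroids on severity and sets no wait, but it states no start time either.
- *That Table 6 omits steroids for grade 4 colitis.* The blank cell may be a PDF-reading artefact, and general instruction 3 covers life-threatening events.
- *That subjects would stay on pembrolizumab through severe colitis.* Table 6 and Sections 5.4.1 and 9.1 say otherwise.

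The reply does not explain the inversion. If time for diagnostic work-up were the reason, the more severe grade would not need more of it, and 9.5.1 already limits the treatment guidance to events judged related to pembrolizumab. Nor does it explain why none of the other five grade 3-4 steroid instructions carries a wait.

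**Conclusion.** The point holds as an inconsistency in safety guidance that should be fixed. Within 9.5.2 the grade 3-4 trigger is 4 days longer than the grade 2 trigger, and it is the only wait among six comparable instructions. It fits neither the severity basis of Section 7.12 nor the absence of a persistence condition in Table 6.

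The harm is conditional on a physician using the bullet as the trigger. The delay would then exceed a week. How many subjects this could reach is not known, because the documents give no colitis rate for this regimen. Section 5.4.1 reports no grade 3 or greater toxicity attributed to the study agents at the review before the 11th arm 2 subject. A reader might take this as a threat to the trial's results, but nothing here touches the primary endpoint, the sample size or the analysis.

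Confidence is high on the mismatch in wording. It is lower on the practical consequence, which depends on how physicians read a suggested measure and on what the ECI document says.

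**What to change.** In the grade 3 or 4 diarrhea/colitis bullet of Section 9.5.2, delete the condition that the event must persist for more than a week and leave the rest unchanged. IV steroids followed by high-dose oral steroids then apply on grade alone, as for the other grade 3-4 events.

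Do not add a general sentence making Table 6 prevail over Section 9.5. Table 6 gives no start time, so the sentence would not settle timing. It would also reach beyond colitis: for grade 3-4 hyperthyroidism, 9.5.2 gives IV then oral corticosteroids, whereas the Table 6 row lists only beta-blockers or thionamides. A blanket rule would cloud that steroid instruction.

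Leave the grade 2 three-day condition to the clinical team. It has no counterpart in Table 6, but time to exclude infection is a defensible reason for it. Check the ECI guidance document for the same one-week wording.

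The cost is one wording amendment. Under Section 13.5 it needs approval by the institutional Clinical Research Review Committee and the IRB, and notification of the FDA because the study runs under an IND. It adds no procedures, visits or subjects.

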9.5.3 Expected AEs from Ferumoxytol and Guidelines for Management

Possible risks and side effects of the study agent ferumoxytol from the Ferumoxytol Investigator's brochure 2012 are below. There will be no dose limitations or modifications to ferumoxytol. If subject experiences a grade 2 or greater allergic or anaphylactic reaction (CTCAE v 4.0) that is directly attributable to the ferumoxytol, the subject will be removed from study.

In Phase III clinical studies in subjects with iron deficiency anemia and chronic kidney disease, the most commonly reported side effects ($\geq 2\%$ of subjects) following treatment with ferumoxytol were diarrhea, nausea, dizziness, hypotension, constipation, and peripheral edema.

Pharmacological class effects commonly associated with marketed IV iron products include hypotension and hypersensitivity reactions. In clinical studies of ferumoxytol, hypotension was reported in 1.9% (33/1726) of subjects. Three of these subjects (0.2%) had related serious hypotensive events, one of which was characterized as an anaphylactoid reaction. All of the events resolved on the same day of occurrence without sequelae. Serious hypersensitivity reactions have been observed in 0.2% (3/1726) of subjects following administration of

ferumoxytol. Other adverse reactions potentially associated with hypersensitivity, including pruritus, rash, urticaria, or wheezing were reported in 3.7% (63/1726) of subjects; each of these reactions occurred in <1% of subjects exposed to ferumoxytol.

The overall incidence of AEs in a post-marketing study irrespective of relationship to study medication was lower in subjects administered ferumoxytol (48%) than in those treated with iron sucrose (65%). The incidence of SAEs was higher in ferumoxytol-treated subjects than in iron sucrose-treated subjects (9% vs 7%). The incidence of related SAEs was similar between the two treatment groups (1% in both groups). The most common AEs among ferumoxytol-treated subjects were nausea (7.5%) and muscle spasms (5.0%).

In the Phase II imaging study where ferumoxytol was used as an imaging agent (doses 1.0, 2.5 and 4.0 mg/kg) in subjects with peripheral arterial disease (PAD), there was a possible dose dependent increase in overall TEAEs reported in this study. Only 3.5% of the subject population experienced TEAEs that were related to ferumoxytol. The majority of the treatment-related AEs were mild in severity and were resolved. 6.1% of the subject population experienced SAEs that were eventually resolved; none were treatment related. There were 3 AESIs reported in 3 subjects (2.6%); 1 subject in each dose group experienced 1 AESI. In the 1.0 mg/kg dose group 1 subject experienced acute hypotension. In the 2.5 mg/kg dose group 1 subject experienced a hypersensitivity reaction of rash, and in the 4.0 mg/kg dose group 1 subject experienced a drug hypersensitivity reaction (acute hypersensitivity reaction to ferumoxytol).

Given the potential for hypersensitivity and other adverse reactions observed with other IV anemia therapies, subjects should be monitored for signs and symptoms of hypotension and hypersensitivity following administration of ferumoxytol as outlined in study protocols. Ferumoxytol should only be administered when personnel and therapies are immediately available for the treatment of anaphylaxis and other hypersensitivity reactions.

With certain IV iron preparations, mild to severe low blood phosphorus levels (hypophosphatemia) have also frequently been reported following administration, particularly in women with heavy AUB. Mild to moderate, asymptomatic reductions in blood phosphorus levels have been infrequently observed following ferumoxytol administration.

Elemental iron is essential for normal cell and tissue development, as well as for tumor cell growth. There are no clinical data to suggest that therapeutic IV iron supplementation, given to correct anemia, stimulates tumor development, despite the theoretical risk. While free iron has been implicated in increased oxidative stress, which is potentially associated with cellular damage and carcinogenesis, there are no clinical studies to support that transient increases in oxidative stress resulting from iron supplementation result in increased tumor growth.

Other potential risks to subjects receiving ferumoxytol include the temporary discomfort at the site of injection, as well as the potential for bruising, local infection, and pigmentation following IV administration.

There are no studies of ferumoxytol in pregnant women, and the risk to a pregnant mother and unborn baby is unknown. In animal studies, ferumoxytol caused fetal malformations and decreased fetal weights at maternally toxic doses of 6 times the human daily dose. Thus ferumoxytol should only be used during pregnancy if the potential benefit justifies the potential risk to the fetus.

It is also unknown whether ferumoxytol is present in human milk. Animal studies showed that when administered daily to pregnant and lactating females, a small amount of ferumoxytol was excreted into breast milk. Because many drugs are excreted in human milk and because of the potential for adverse reactions in nursing infants, a decision should be made whether to discontinue nursing or to avoid ferumoxytol, taking into account the importance of ferumoxytol to the mother and the known benefits of nursing.

No data from clinical trials are available regarding overdose of ferumoxytol in humans. During the post-marketing phase, several subjects received an overdose of ferumoxytol ranging from 1 g in 1 day to 2.5 g over 14 days. Only one case of minor rash was observed.

Although this section provides general guidance regarding the risks and side effects associated with administration of ferumoxytol, investigators should refer to the protocol for study-specific follow-up and the monitoring procedures.

9.6 Additional IND Reporting Requirements for Ferumoxytol

Sponsor-investigator of this IND is responsible for compliance with the FDCA (21 U.S.C. §§ 301 et. seq.) as well as the implementing regulations [Title 21 of the Code of Federal Regulations (CFR)]. Responsibilities include:

- Reporting any unexpected fatal or life-threatening suspected adverse reactions to this Division no later than 7 calendar days after initial receipt of the information [21 CFR 312.32(c)(2)]. If IND is in eCTD format, submit 7-day reports electronically in eCTD format. If IND is not in eCTD format, submit 7-day reports by telephone or fax;
- Reporting any (1) serious, unexpected suspected adverse reactions, (2) findings from other clinical, animal, or in-vitro studies that suggest significant human risk, and (3) a clinically important increase in the rate of a serious suspected adverse reaction to this Division and to all investigators no later than 15 calendar days after determining that the information qualifies for reporting [21 CFR 312.32(c)(1)]. If IND is in eCTD format, submit 15- day reports to FDA electronically in eCTD format. If IND is not in eCTD format, submit 15-day reports in paper format; and
- Submitting annual progress reports within 60 days of the anniversary of the date that the IND went into effect (the date clinical studies were permitted to begin) [21 CFR 312.33].

